We will stratify based on education level to be largely representative of the UK population (14, 15). We will recruit (approximately):

- 50% NQF 4 Level 4 or above (University degree or equivalent) and 50% NQF Level 3 or below (no University degree)

We will also aim to fulfil the following quotas for age and gender, based on the composition of the UK population (16, 17):

- 50% 18 – 39 and 50% 40 and over
- 50% female and 50% male

We will only recruit up to 10% of the sample as current University students. Students have a high SEP in terms of education, but typically have low disposable income, which may impact relative health motives. This could distort the results if students are recruited in high numbers.

Inclusion and exclusion criteria

Participants are eligible to take part if they:

- Are a UK resident
- Are aged 18 years and above
- Are fluent in English
- Eat an out-of-home meal at least once a month on average
- Have no dietary allergies
- Are not vegan

There are no additional exclusion criteria as this is a real-world study.

Methods

Procedure

Participants will be asked to attend one session at a restaurant from Monday – Saturday between 12 – 5pm. All participants will be asked to verbally consent to taking part in the study, and will be given the opportunity to ask questions before the study begins.

Participants will be asked to order lunch from a menu. The menu will either feature nutrient warning labels next to the relevant menu items (experimental condition), or no labels (control condition). A researcher will ask participants to write their order down on an order form, communicate the order with the kitchen, photograph the meal when it is ready to be served, and photograph the plate when the participant is finished with the meal in order to estimate amount consumed.

After finishing their meal, participants will be asked to fill out an online questionnaire (on an iPad) about their sociodemographic characteristics, health motives, label awareness, salt awareness, perceived message effectiveness, perceived knowledge gain, perceived influence, and support for the introduction of a restaurant salt warning label policy in the UK. The questionnaire will also ask (i) whether any food or drink items were shared with other participants, and, if so, what item(s) were shared and (ii) whether they added any condiments to their meal (see Appendix E).

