Participants will receive a link to a dietary recall questionnaire (Intake24, <https://intake24.co.uk/>) via email the next morning after taking part in the study, which they will be prompted to complete before midnight that day. They will be asked to provide as much detail as possible on what they had for dinner, snacks, and drinks after the restaurant visit. Based on this information and salt values calculated by Intake24, we will estimate the total salt consumed by the participants for the rest of the day after the visit.

Other macronutrient intake

Total kcal, sugar, and saturated fat intake [i.e., other nutrients that are not the main warning focus] will be calculated based on the nutritional content of the order of the participant.

Additional measures

Food choice motives

The “health” subsection of the Food Choice Questionnaire (29) will be used to measure the extent to which health motives may influence participants’ food choices. The subsection consists of 6 items, e.g. “It is important to me that the food I eat on a typical day....is nutritious” answered on a 4-point Likert scale ranging from “Not at all important” to “Very important”. We will calculate the mean response for the six items.

Aim guessing

Participants are told that the study is about dining habits in restaurants. At the start of the post-meal assessments, participants will be asked what they think the aims of the study were (free text response). Any participant that guesses the study aims to be investigating the influence of food warning labels on food choice will be coded as being aware of study aims. One researcher will code awareness of aims ([name]) and a second researcher will independently verify the coding.

Study flow

Recruitment	
 - Participants will be recruited via online adverts, word of mouth, and an existing participant database maintained by researchers at the University of Liverpool. - A link to the screening questionnaire will be provided. (Appendix A) - Participants will be stratified by SEP, age, and sex. 				

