Reimbursement	
 - Participants will receive £25 which will likely cover their lunch costs and serve as an incentive for people from different SEP strata to participate. Participants will either (i) pay for their own meal at the restaurant and receive £25 via invoice or (ii) have their meal paid for by a researcher using a prepaid card; if this costs less than £25, they can request to receive the remaining amount via invoice, if this costs more than £25, they will need to pay the difference at the restaurant. 	

Statistical analysis

Participant characteristics

Participant characteristics will be presented overall and by experimental condition in a table. Data will include age, gender, ethnicity, highest educational qualification, employment status, BMI, frequency of eating OOH, and hunger. Continuous variables will be summarised as means and standard deviations, and categorical variables will be summarised as counts and percentages.

Measured variables

Primary

A linear regression will be used to assess differences between menu conditions in terms of PME. The between-subjects predictor will be label condition, and the dependent variable will be PME.

Highest education level (categorical: NQF level 4 or above, NQF level 3 or below) will be included as a covariate in the model to account for stratification (30). Health motives (continuous) will be included as a covariate as this may predict outcomes (e.g., health motivated individuals may be more likely to believe a menu with labels will change their behaviour) (30). Age and gender will also be included as covariates as previous work suggests that this can influence ratings of label PME and salt intake (13).

Descriptive analysis will be used to report (overall and by condition) participants' label awareness, salt awareness, perceived knowledge gain, perceived influence, and policy support (dichotomised into support/oppose). Logistic regressions will be performed to assess the odds of (i) being aware of the label, and (ii) being aware of the salt content of the meals in the labelled menu group, using the control menu group as the reference category. The same covariates as above will be included.

Secondary

Linear regressions will be performed to assess differences in menu conditions in terms of total salt purchase and total salt intake. The same covariates as above will be included.

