A logistic regression will be performed to assess the odds of selecting a high salt meal in the labelled menu group, using the control menu group as the reference category. The same covariates as above will be included.

As some participants are likely to bring guests to the restaurant and guest tables are the unit of randomization, there may be clustering for outcome variables (i.e., the variation in PME and/or salt purchase/intake may be partially explained by table). We will test for clustering effects by comparing the within-table variability for outcome variables to the between-table variability. We will use the likelihood ratio test to ascertain the difference in likelihoods between the two. If this is statistically significant ($p < .05$) then there is enough evidence to suggest that there is a clustering effect of table groups eating together. If there is evidence of clustering then we will perform a series of linear mixed model analyses, with label condition as an independent variable, and table group as a random effect for primary and secondary outcomes.

Exploratory analyses

Linear regressions will be performed to assess differences in menu conditions in terms of later salt intake, and intake of other macronutrients. This is to examine whether individuals engage in any compensatory eating behaviour after seeing the labels (e.g., they are aware that they consumed a

high salt meal and therefore reduce their salt intake later in the day), or whether intake of other macronutrients (e.g., calories) is impacted. Again, the same covariates as above will be included.

Sensitivity

Sensitivity analyses will be conducted to test if results are the same after removing any participants that correctly guess the aims of the study (i.e., the effect of salt warning labels on food choice, or similar). If many participants identify the study aims (e.g., > 25%) we will examine if study aim awareness status moderates any effects of labelling by including this as a covariate (categorical) in analyses. Any deviations in findings from the main analyses will be reported.

Missing data

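### Later salt intake is totalled over a window whose length depends on visit time (a spread of up to about 4–5 hours between tables), and its exploratory regression does not adjust for visit time

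*Combined protocol and SAP*

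**What the plan says.** On timing, the Procedure section states: "Participants will be asked to attend one session at a restaurant from Monday – Saturday between 12 – 5pm". The Study flow table adds that the researcher schedules visits with half-hour gaps between groups, and that everyone at a table shares one condition. Visit time therefore varies between tables and is common to everyone at a table.

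On the outcome, the Later salt intake section says participants report "what they had for dinner, snacks, and drinks after the restaurant visit", and that "we will estimate the total salt consumed by the participants for the rest of the day after the visit". It sets no fixed number of hours and no rate per hour.

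On the analysis, the Exploratory analyses section says: "Linear regressions will be performed to assess differences in menu conditions in terms of later salt intake, and intake of other macronutrients". It then adds: "Again, the same covariates as above will be included". Those covariates are set out under the primary analysis: "Highest education level (categorical: NQF level 4 or above, NQF level 3 or below) will be included as a covariate"; "Health motives (continuous) will be included as a covariate as this may predict outcomes"; and "Age and gender will also be included as covariates". Visit time is not among them. The Intervention section, which describes randomisation in blocks of 50, does not mention stratifying by it either. The Missing data section says missing later intake will be imputed, without naming the variables in the imputation model.

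**The concern.** The outcome is a sum over a window that opens when the visit ends and closes with the day. A table seated at noon has the afternoon and the evening meal ahead of it. A table seated late in the afternoon has fewer hours left, and its meal may stand in for dinner. The same total can therefore mean different things at different tables.

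This regression is the plan's only test of whether diners compensate for a salty lunch later in the day, and it is run at the stricter .01 level. If visit time predicts later salt, leaving it out has two costs. Its variance stays in the residual, and it sits between tables, where it reduces precision most. Any chance difference between the arms in mean visit time also passes into the estimated label effect.

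**Working it through.** **The plan's own figure.** The Sample size section gives 260 (130 per condition) for d = 0.35, 80% power, two-tailed, with alpha .05. The normal approximation gives 2 × (1.960 + 0.842)² / 0.35² = 128.1, so 129 per arm. The t-test gives 129.1, so 130 per arm and 260 in total. The figure is reproduced. It is stated for PME, salt purchased and salt intake. No effect size or power is stated for later salt intake.

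**Spread of the window.** If 12–5pm is the range of start times, the spread is 17 − 12 = 5 h. If a session of about 1 h (assumed) must end by 5pm, it is 4 h.

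**Inputs not in the documents (assumed).** Slots are spread evenly, residual SD is 2 g, and later salt falls by b = 0.1 to 0.5 g per hour of later start. The upper end is close to a whole-day average. The Background puts adult intake 40% above 6 g, and 6 × 1.4 = 8.4 g. Over 16 waking hours (assumed) that is 8.4 / 16 = 0.525 g/h.

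**Share of variance explained by visit time.** For a range of W hours, the variance of visit time is W²/12: 25/12 = 2.083 h² for 5 h and 16/12 = 1.333 h² for 4 h. The share is b²W²/12 divided by (4 + b²W²/12).

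| b (g/h) | 5 h range | 4 h range |
|---|---|---|
| 0.1 | 0.021 / 4.021 = 0.5% | 0.013 / 4.013 = 0.3% |
| 0.3 | 0.188 / 4.188 = 4.5% | 0.120 / 4.120 = 2.9% |
| 0.5 | 0.521 / 4.521 = 11.5% | 0.333 / 4.333 = 7.7% |

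**Chance imbalance between arms.** With m people per table and 130 per arm, the SD of the difference in mean visit time is √(W²/12) × √(2m/130). Over 5 h, with √2.083 = 1.443 h:

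- m = 2: 1.443 × 0.175 = 0.25 h
- m = 4: 1.443 × 0.248 = 0.36 h
- m = 10 (the largest table allowed): 1.443 × 0.392 = 0.57 h

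For tables of four, a 1-SD imbalance shifts the estimated label effect by 0.36 × 0.1 = 0.04 g to 0.36 × 0.5 = 0.18 g. On the assumed 2 g SD that is 0.02 to 0.09 SD.

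**The case against.** The strongest reply is that the size rests almost wholly on assumption. Only the 6 g limit, the 40% excess and the visit hours come from the documents. The whole-day average of about 0.5 g/h includes breakfast and lunch, whereas the recall covers dinner, snacks and drinks after the visit. If most tables eat dinner afterwards, whatever their slot, salt need not scale with hours and the slope could be near zero. This stands. It is why the range starts low and why visit time cannot be called a strong predictor.

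A reader might also infer that the label comparison is biased. The documents do not support that. Tables are randomised, so visit time is balanced in expectation, and any omitted prognostic variable leaves the same exposure to chance imbalance.

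The stakes are also limited. Later salt intake is described under Secondary outcomes but analysed as exploratory. It is not named in the objectives, and the interim decision does not use it. This too stands.

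Finally, a linear hourly term would capture only part of a step effect, such as a late lunch replacing dinner. It would also leave any other correlation within tables unmodelled. The conditional random effect for tables is written for primary and secondary outcomes, so whether it reaches this analysis is unclear. These points limit what the covariate can do but give no reason to omit it.

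**Conclusion.** The point holds as a minor improvement to one exploratory analysis. The window for later salt intake differs between tables by up to about 4–5 hours, and no planned term accounts for it. The consequence is lost precision and exposure to chance imbalance.

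Under the assumptions above, visit time would explain about 0.5–12% of the variance over a 5-hour range and about 0.3–8% over 4 hours. These figures are illustrative: slope, SD and spread of slots are all assumed, 5 hours is a ceiling, and the true effect could be close to nil. Reading the omission as an error that undermines the trial's conclusions would go too far. PME, the other secondary outcomes and the sample size of 260 do not depend on it.

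**What to change.** Pre-specify booked session start time (hours, continuous) as an additional covariate in the later-salt-intake regression, and include it in the imputation model for missing recalls. Use the booked time rather than the finishing time. It is set before anyone at the table sees a menu, whereas finishing time could be affected by the menu. It is also known for participants who do not return the recall, so it can inform their imputed values.

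The cost is one sentence in the analysis plan and one column in the data set. The researcher already schedules each visit, so participants are asked for nothing more. The order form in Appendix D has no time field, so the booked time should be carried over from the schedule. The change should be made before outcome data are examined by condition, so that it is not a post hoc choice.

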To date, the impact of nutrient warning labels has not been tested in a real-world randomised controlled trial (i.e., in a restaurant), or in a UK context. Recent work suggests that UK consumers support the introduction of nutrient warning labels, and their PME was rated as significantly higher relative to a control label (QR code) (13). This study aims to test the effect of a menu featuring salt warning labels (design informed by previous work (13)) on perceived message effectiveness relative to a menu with no labels in a real-world restaurant environment. The study will also act as a pilot experiment for examining the impact of the salt warning label on food choice and subsequent salt intake in real-world conditions.

Primary objectives:

- To measure the PME of a menu featuring salt warning labels relative to a menu with no labels
- To measure label awareness, perceived knowledge gain, and perceived influence of the label on food choice

Secondary objectives:

- To identify whether there is an effect of the salt warning label on:
 - Food choice (label/no label)
 - Total salt selected
 - Total salt intake
- To examine support for the introduction of a salt warning label policy in the UK

Experimental design

The study will be a between-subjects randomised controlled trial design. The between-subject factor is the menu labelling. In the experimental condition, a nutrient warning label will be placed next to menu items that are high in salt. In the control condition, there will be no labels. The outcome will be (i) perceived message effectiveness, (ii) salt selected, label (y/n) selected, and salt intake. This will allow us to examine whether the salt warning label intervention impacts perceived message effectiveness and food choice relative to the control condition.

Participants and recruitment

Recruitment

Participants will be recruited via social media adverts (Facebook, Instagram), a database maintained by researchers at the University of Liverpool, and word of mouth. Interested participants will be asked to click a link which will take them to an online screening questionnaire (Appendix A). Participants can bring a maximum of nine guests to the restaurant. Guests will be pre-screened in advance to ensure eligibility. In pre-study instructions participants will be informed that any guests they bring will participate in the study.

Sampling

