PME will be measured using an adapted version of the UNC PME scale. The scale measures health concern, product attitude, and discouragement of product consumption (21). Participants will answer 3 PME questions using a Likert scale ranging from 1 – 5 anchored by “not at all” and “a great deal”: Prompt: “Think back to the menu that you ordered from...” “The menu made me concerned about the health effects of consuming items high in salt”, “The menu made consuming items high in salt seem unpleasant”, “The menu discouraged me from wanting to consume items high in salt”. The mean response to the three items will be calculated. PME is used as an early indicator of a health message’s potential to change behaviour (e.g., reduce selection of items high in salt) (22). The scale has been used extensively in similar experiments to identify the potential impact of nutrient warning labels, has strong construct validity, and is predictive of longer-term actual behaviour (21, 23-28).

An attention check will be placed after the PME questions. “This question is an attention check, so please answer truthfully. How many times have you visited the planet Mars? Several times / Just once / Never”.

Correct answer: Never

Label awareness

"Did you notice any warning labels next to any of the menu items when making your meal selection?" (yes/no).

If [yes], "What did the label tell you about?" Response options: Healthy items, Organic, Calcium, Sustainable, Added sugars, Vegetarian, Unhealthy items, Salt, Fibre, Gluten Free, None of these, Not sure.

If [yes], "Please describe what the label said" (open text response). Responses that mention high in salt or similar will be coded as aware.

Salt awareness

"Did you think about the salt content of the meals when making your selection?" (yes/no)

Note: For the below questions, both groups will be shown an image of the labelled menu. Some question phrasing is slightly altered for the control condition.

Perceived knowledge gain

"Did you learn something new from the salt labels on the menu?" (yes/no).

Control: Same as above

Perceived influence

"Did the salt label influence which food you ordered from the menu" (yes/no).

"If [yes], how did the salt label influence your choice?" Response options: I avoided choosing a meal high in salt; I chose a meal high in salt; Other (free text response)

Control: "Would the salt label have influenced what food you ordered from the menu?" (yes/no)

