Appendix E – Post-exposure assessments

Please enter your participant ID. If you are unsure what this is, please ask the researcher.

Please select the letter which is circled on your sticker label. If you are unsure, please ask the researcher.

A (1)

B (2)

End of Block: Default Question Block

Start of Block: Aim guessing

What do you think was the aim of this study?

End of Block: Aim guessing

Start of Block: Food sharing

Did you share any of the food or drink items?

Yes (1)

No (2)

Display This Question:

If Did you share any of the food or drink items? = Yes

What items were shared? Please also give an estimation in % of how much of each item was shared.

Did you add any condiments (e.g., sauce, salt) to your food?

- Yes (1)
- No (2)

Display This Question:

If Did you add any condiments (e.g., sauce, salt) to your food? = Yes

What condiments did you add? Please also give an estimation in teaspoons of how much of each condiment was added.

End of Block: Food sharing

Start of Block: PME

Please consider the following statements in relation to the menu you ordered from.

Not at all (1) A little bit (2) Somewhat (3) Quite a bit (4) A great deal (5)

The menu made me concerned about the health effects of consuming items high in salt. (1)

The menu
made
consuming
items high in
salt seem
unpleasant. (2)

The menu
discouraged
me from
wanting to
consume
items high in
salt. (3)

 End of Block: PME**Start of Block: Attention check**

This question is an attention check, so please answer truthfully. How many times have you visited the planet Mars?

- Several times (1)
- Just once (2)
- Never (3)

End of Block: Attention check**Start of Block: Awareness**

Did you notice any warning labels next to any of the menu items when making your meal selection?

- Yes (1)
- No (2)

Display This Question:

If Did you notice any warning labels next to any of the menu items when making your meal selection?

= Yes

What did the label tell you about?

Healthy items (1)

Organic (2)

Calcium (3)

Sustainable (4)

Added sugars (5)

Vegetarian (6)

Unhealthy items (7)

Salt (8)

Fibre (9)

Gluten free (10)

None of these (11)

Not sure (12)

Display This Question:

If Did you notice any warning labels next to any of the menu items when making your meal selection?

= Yes

Please describe what the warning label said.

Page Break

Did you think about the salt content of the meals when making your selection?

Yes (1)

No (2)

End of Block: Awareness

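### Label awareness is coded from an open-text answer that follows, on the same page, a 12-option list including Salt, so a prompted answer can count as awareness

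*Combined protocol and SAP*

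**What the plan says.** The primary objectives include this one: "To measure label awareness, perceived knowledge gain, and perceived influence of the label on food choice". The Label awareness entry under Primary outcomes has three parts.

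- A yes/no gate: "Did you notice any warning labels next to any of the menu items when making your meal selection".
- If yes, a closed question, "What did the label tell you about", with this list: "Response options: Healthy items, Organic, Calcium, Sustainable, Added sugars, Vegetarian, Unhealthy items, Salt, Fibre, Gluten Free, None of these, Not sure".
- If yes, an open-text description of the label.

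Only the third part has a coding rule: "Responses that mention high in salt or similar will be coded as aware". The plan gives no coding use for the list answer and no rule for discounting prompted answers.

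Appendix E keeps this order. In the Awareness block the list comes first and "Please describe what the warning label said" follows, both shown on the same condition (a yes at the gate). The only page break marked in the block comes after the open text.

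The Statistical analysis section reports awareness overall and by condition and adds a model: "Logistic regressions will be performed to assess the odds of (i) being aware of the label", comparing the labelled menu with the control menu.

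**The concern.** A free description adds something to a yes/no answer and a list when it shows what the diner took from the label without help. Here the content is displayed just above the box. A diner who saw that some label was present, but not what it said, has the word salt in view while writing. The rule's allowance for similar wording probably lets a bare mention of salt count.

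The figure at stake is the proportion of diners in the labelled arm who registered the message. A policy reader would take that from this trial as evidence on whether such labels are read. Prompting raises it and mixes diners who read the label with those who only saw that something was there. Control menus carry no labels, so any control diner coded aware is a false positive, and the same prompt can produce those too.

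**Working it through.** **Plan's own figure.** There is none. The documents give no expected awareness rate, effect size or power for this outcome. The check is therefore of item order, followed by an illustration.

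**Item order in Appendix E.**
1. Aim guessing.
2. Food sharing and condiments (salt is named here, as an example of a condiment).
3. The three PME items, each referring to items high in salt, for example "The menu made me concerned about the health effects of consuming items high in salt".
4. Attention check.
5. Awareness block: gate, 12-option list with Salt as option 8, open text, page break, salt-awareness question.
6. Additional assessments, where both arms see the labelled menu. This comes after the awareness answers and cannot cue them.

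So two salt cues bear on the open text: the PME wording, seen earlier by everyone, and the list, seen immediately before by those who said yes. The Study flow table also puts PME before label awareness.

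**Illustration, labelled arm.** All three inputs are assumptions:
- N = share who say they noticed a label, 0.4 to 0.8.
- K = share of those who truly recall its message, 0.5 to 0.9.
- c = share of the remainder who write salt because they were prompted, 0 to 1.

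Coded aware = N×K + N×(1−K)×c, so the excess is N×(1−K)×c. Counts use 130 diners per condition, from the Sample size section.

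| c | Excess, percentage points | Excess of 130 | Coded aware at N = 0.6, K = 0.7 |
|---|---|---|---|
| 0 | 0 | 0 | 42% |
| 1/12 (random pick) | 0.3 to 3.3 | 0.4 to 4.3 | 43.5% |
| 0.25 | 1 to 10 | 1.3 to 13 | 46.5% |
| 0.5 | 2 to 20 | 2.6 to 26 | 51% |
| 1 | 4 to 40 | 5.2 to 52 | 60% |

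The lower end of each range is N = 0.4, K = 0.9; the upper end is N = 0.8, K = 0.5. Example: 0.6×0.7 + 0.6×0.3×0.5 = 0.42 + 0.09 = 0.51.

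**Illustration, control arm.** True awareness is zero. Let f be the share who wrongly say they noticed a label, assumed 5% to 20%. Coded aware is f×c.
- c = 0.25: 1.25% to 5%, or 1.6 to 6.5 of 130.
- c = 0.5: 2.5% to 10%, or 3.2 to 13 of 130.

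With N = 0.6 and K = 0.7 in the labelled arm and the same c in both arms, the crude odds ratio is 68.7 to 16.5 at c = 0.25 and 40.6 to 9.4 at c = 0.5. For example, (0.51/0.49)/(0.10/0.90) = 9.4. With c = 0 there are no control events and the odds ratio cannot be estimated. In this illustration more prompting raises the labelled-arm proportion but lowers the odds ratio.

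**What reordering removes.** Only the part of c due to the list. If, as an assumption, c fell from 0.5 to 0.25, coded awareness would fall from 51% to 46.5%. The remaining 4.5 points above 42% would be due to other cues, including the PME wording.

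**The case against.** The strongest reply is that the list is the weaker of the two cues. By the time diners reach it they have read the PME wording three times, and that wording is close to the label's own text. This stands. It means that reordering the Awareness block cannot yield uncued recall, and a reader who inferred that it would do so would be wrong. Moving awareness ahead of PME is not a free alternative, because it could prime PME, the outcome that the study is powered on.

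A reader might also infer that the list hands over the answer. The documents do not support that: Salt is one of 12 options, nothing marks it as correct, and the options include None of these and Not sure. The list is a prompt.

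Nor does the plan say that the description is meant as unaided recall. That purpose is inferred from the free-text format and the coding rule.

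A single size is equally unsupported. Taking N = 0.60, 1−K = 0.20 to 0.40 and c = 0.5 gives 6 to 12 points. The same inputs with a random pick give 0.60 × (0.20 to 0.40) × 1/12 = 1 to 2 points, and with no prompting they give zero.

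Finally, the plan already collects what is needed to see the problem: the gate answer precedes the list and is untouched by it, the list answer is stored, and control diners receive the same items. This stands too and shapes the remedy, but the plan does not commit to reporting the three answers separately.

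**Conclusion.** The point holds as a minor measurement weakness. Awareness is coded only from text written directly after, and on the same page as, a list naming salt. Some diners who noticed a label but not its message can therefore be coded aware, in either arm.

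The size is unknown and could be near zero. It depends on how many such diners there are, how many are prompted, and whether a bare mention of salt counts under the coding rule. The labelled-arm proportion can only be pushed up by this mechanism. The direction for the odds ratio is not determined, because it depends on false positives among control diners.

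The same-page statement rests on the layout printed in Appendix E. If the live survey shows one item per screen, the list still comes first. A reader might infer that the trial's main results are compromised. They are not: the yes/no noticing answer, PME and the food-choice and salt outcomes do not depend on this item order.

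**What to change.** 1. Within the Awareness block, place the open text directly after the gate, on its own page with no back button, and show the list on the next page. Code awareness from the open text, and state whether a bare mention of salt counts.
2. Leave the PME items where they are. Describe the coded result as recall after the PME items, not as uncued or unaided.
3. Report three results separately by arm: the yes/no noticing answer, the open-text coding, and recognition from the list. Read control-arm aware codes as the false-positive rate, and show how many control diners passed the gate, since fewer of them may reach the open text than in the labelled arm.

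The cost is a swap of two survey items and one page break, with no new question, no added burden on diners, no change in sample size and no loss of data. If the questionnaire is already in use, step 3 can still be done without changing it. The open-text result should then be called prompted recall.
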